Intervention Description: The intervention will be administered by a trained interventionist who has participated in ENRICH/ECHO, an oncofertility communication training program. The interventionist will administer the digital FP Decision Tool to families in the intervention arm and will facilitate a guided discussion about responses and discrepancies. The FP Decision Tool asks 25 questions examining each AYA's thoughts or feelings regarding parenthood and fertility preservation. The parent version asks the same 25 question, plus an additional 9 questions asking the parent to rate their son's feelings on certain topics (i.e. whether their son wants to have a child, whether their son would be as happy with an adopted child versus a biological child). Items are coded based on the domains of the HBM (perceived benefits, perceived barriers, perceived threats, self-efficacy, and cues to action). The decision tool was developed using the HBM and is based on factors associated with FP uptake and decision quality in the literature, as well as new factors identified in the preliminary work of this research group.

AYAs and parents independently complete the electronic tool; an automated Quick View report is generated, highlighting misconceptions and parent-AYA discrepancies. The interventionist uses this information to facilitate a conversation with AYA and their caregiver(s). Specifically, the interventionist uses standardized prompts/language to: 1) address knowledge gaps/misconceptions, 2) share participants' fertility-related values and goals with one another*, 3) highlight discrepancies between responses*, and 4) promote family communication and consensus building. The facilitated conversation will be audio recorded.

Intervention Rationale: The intervention is designed to take participant's answers and provide a conversation tailored to their questions and needs. It will be carried out by one interventionist that has completed ENRICH/ECHO (oncofertility communication) training to ensure the intervention will not unnecessarily burden patients and families. Additionally, the intervention is designed to be short (less than 20 minutes). It is expected that participants will be present for the entire intervention in order to have their baseline data included in analyses.

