- *Informed Consent:* Informed consent (and assent for participants 12-17 years of age) is obtained by study staff before data collection procedures or randomization. For adolescents between 12-17 years of age, informed consent will be obtained by a parent or legal guardian, and assent will be provided by the adolescent. Those who are between 18-25-years of age will provide informed consent for themselves to participate.
- *Demographics:* Research staff ask participants to answer questions about age, race, ethnicity, religion, education, income, whom they live with, and their relationship to their child. AYAs will be asked to answer an additional four questions about their communiation with their parents. These questions were taken from the Parent-Adolescent Communication Scale (PACS).
- *Randomization:* Families who consent to participate will be randomized (by the interventionist) to the control arm or intervention arm (family-centered psychoeducational intervention) after completing baseline measures. If the family is randomized to the control arm, the interventionist will inform the family that they were randomized to the control group and debrief the family. If the family is randomized to the intervention arm, the interventionist will inform the family that they are conduct the interventionist will inform the family that randomized to the treatment group and conduct the intervention immediately following randomization.

1-month Follow-up (Visit 2, Baseline + 1 to 2 months): At the 1-month follow-up (Visit 2) research staff will contact control and intervention families in-person (at inpatient or outpatient clinic) or via phone or email. Families (AYAs and parents) will be reminded about the study and be asked to complete follow-up activities. All measures will be completed by the child and both caregivers (when available). If the child and/or second caregiver did not complete Visit 1, they will be invited to complete Visit 2. The activities completed at Visit 2 include:

- *FP Decision Survey:* Participants will complete a brief survey about their FP decision. Items will include questions such as who participants talked to about their FP decision and who made the final decision regarding FP. Surveys will not be scored but questions will be used to guide analyses.

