Data Collection Procedures: Data described in Section 6.0 will be collected for all participants. Data will be collected by trained research staff using an online survey tool (e.g., REDCap) or paper and pen questionnaires. Some data may be obtained from the participant's electronic medical record. Data collected at Visit 1 will be collected before the intervention begins, and data collected at Visits 2 and 3 will be collected after the intervention ends.

End of Study Definition: A participant is considered to have completed the study if they completed the baseline assessment, as well as the 1-month and 1-year follow-up assessments.

Lost-to-Follow-up Definition: A participant will be considered lost to follow-up if they fail to return for scheduled visits and study staff are unable to contact the participant after at least 3 attempts via phone or email.

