15.0 Risks to Subjects*

It is expected that completing study questionnaires and interviews will introduce minimal risk to participants, yet the study team acknowledges that the new cancer diagnosis will be a stressor for AYAs and parents. Participants may experience some discomfort and/or embarrassment when completing survey items or interviews about FP. Given the study design, all patients and caregivers will have already received information about FP during the clinical fertility consult, per standard of care. Parents or AYAs may experience distress when asked about parent-child communication, although we do not expect this to have severe or long-lasting effects on the respondent. In preliminary work, parents and AYA have completed measures, similar to those in this study, within 10 minutes and provided positive feedback about the experience, emphasizing their perceived importance of addressing this topic. Loss of confidentiality is also a potential risk, although no more so than in any other research study. The study team will take every precaution to prevent this.

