Expectedness: All AEs and SAEs are assessed by the principal investigator, and if necessary, another professional with clinical experience in the study population to determine their expectedness. Expectedness is assessed based on the awareness of AEs and/or SAEs previously observed, not on the basis of what might be anticipated from the properties of the study intervention.

Expectedness of the event is assessed using the categories below:

- Expected: An event is considered expected if the nature, severity, or frequency of the event is consistent with the risk information previously described for the study procedures.
- Unexpected: An event is considered unexpected if the nature, severity, or frequency of the event is not consistent with the risk information previously described for the study procedures.

Time Period and Frequency for Event Follow-up: Research staff record events with occurring after informed consent is given up until the end of the intervention. The occurrence of AEs and/or SAEs may come to the attention of study personnel during study visits, interviews, and questionnaires; or when a study participant presents for medical care.

AEs and SAEs are captured on the appropriate case report form (CRF). Information collected includes event description; time of onset; clinician assessment of severity, relationship to study procedures (assessed only by those with the training and authority to make a diagnosis), expectedness; and time of resolution/stabilization of the event. All AEs and SAEs occurring during the above-mentioned timeframe are documented appropriately regardless of relationship to the intervention. Events are followed for outcome information until resolution or stabilization.

Reporting: AEs are reported to the NCH IRB at least annually. AEs are reported to the DSMB at each meeting. AEs are reported to NCI according to their recommended timelines. Per NCH HRP-103 (updated 12/10/18), SAEs determined to be related to the intervention and unexpected are reported to the NCH IRB within 5 business days of discovery; other SAEs are reported to the NCH IRB annually. SAEs are reported to the DSMB and to NCI according to their recommended timelines.

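### AE and SAE recording closes when a single Visit 1 session ends, with no closing point written for controls, so Section 19.0 leaves out the follow-up visits and conflicts with Section 18.0

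*Combined protocol and SAP*

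**What the plan says.** Section 19.0 (Time Period and Frequency for Event Follow-up) gives the recording rule: "Research staff record events with occurring after informed consent is given up until the end of the intervention". It then says that events inside that period are documented whatever their relationship to the intervention. The period is therefore defined by when an event occurs, not by when staff learn of it. The same paragraph lists visits, interviews and questionnaires among the ways an event may be noticed.

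Section 5.0 (Intervention Rationale) says that "the intervention is designed to be short (less than 20 minutes" is the planned length. Section 6.0 (Randomization, Visit 1) has the interventionist "conduct the intervention immediately following randomization". For controls, "the interventionist will inform the family that they were randomized to the control group and debrief the family"; nothing further is delivered to them. Section 6.0 (Data Collection Procedures) adds that "data collected at Visits 2 and 3 will be collected after the intervention ends".

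Section 15.0 names the study's own procedures as a source of upset: "Participants may experience some discomfort and/or embarrassment when completing survey items or interviews about FP". Of distress from questions on parent-child communication it says "we do not expect this to have severe or long-lasting effects on the respondent".

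Section 18.0 collects safety information at routine interactions, including data-collection points, with no end date, and sends the DSMB a summary that includes adverse events every six months.

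**The concern.** The recording rule ends on the first study day for a family in the intervention arm, while participation lasts about a year and includes two further rounds of surveys and interviews. Those later contacts are among the procedures that Section 15.0 expects to cause discomfort. Distress set off by the session itself, a possibility that Section 14.0 anticipates, is also outside the window if it begins after the session is over. For controls the rule has no meaning, because they have no intervention to end.

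At stake is systematic capture on the AE form, and hence in the DSMB summaries, of mild or expected study-related distress that begins after Visit 1. No efficacy endpoint is affected.

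**Working it through.** The plan gives no figure for the recording window, so there is none to reproduce, and the sample-size calculation does not enter. The check sets sections side by side and then counts contacts.

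**1. When does the intervention end?** Section 5.0 speaks of a session under 20 minutes, and Section 6.0 puts it straight after randomization at Visit 1. Section 5.0 also mentions an intervention phase of the study, which could suggest something longer. The data-collection paragraph of Section 6.0 settles this: Visits 2 and 3 come after the intervention has ended. Both follow-up visits are outside the window on the protocol's own terms.

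**2. What closes the window for controls?** Nothing is written. The nearest equivalent is the debrief at Visit 1. If that is the close, neither arm has AE-form coverage of follow-up.

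**3. Do other passages agree with the rule?**
- Section 18.0 gathers safety information at data-collection points, which include Visits 2 and 3. Section 19.0 need not record an event that begins there.
- Section 19.0 names interviews as a way events are noticed, yet Section 6.0 schedules interviews only at Visits 2 and 3. That sentence concerns detection and does not lengthen the window. An event that began at Visit 1 could be noticed at an interview and recorded; one that began at the interview would be noticed but need not be.

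These passages suggest that longer capture was intended, but the rule as written does not deliver it.

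**4. How many contacts fall outside?** Inputs: 40 AYAs and 70 caregivers (Section 12.0), 20 AYAs per arm (Section 2.0), one interview per participant at each of Visits 2 and 3 (Section 6.0). The split of caregivers between arms is not given.
- Visits covered in the intervention arm: 1 of 3. Interviews covered: 0 of 2.
- Even split (assumption): 20 + 70/2 = 55 participants; 55 × 2 = 110 interviews.
- Range: with at most two caregivers per AYA, one arm has at most 20 × 2 = 40 and at least 70 − 40 = 30. That gives 50 to 60 participants and 100 to 120 interviews.
- With 81% follow-up at both visits: 100 × 0.81 = 81; 110 × 0.81 = 89.1; 120 × 0.81 = 97.2. The 81% is the pilot's Visit 2 rate in Section 2.0, and applying it to Visit 3 is an assumption. Section 13.0 reports 100% engagement at 1 month in earlier work, so the higher figures are also possible.

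The control arm has the same range of interviews, with undefined status.

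**5. Late joiners.** Section 6.0 says: "If the child and/or second caregiver did not complete Visit 1, they will be invited to complete Visit 2". It does not say when such a person consents. If consent is first given at Visit 2 in an intervention-arm family, the window has closed before that person enters.

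**6. Timing of IRB reports.** Section 18.0 sends adverse events to the IRB as they arise. Section 19.0 sends related and unexpected SAEs within 5 business days and all other SAEs once a year. Since Section 19.0 defines an SAE as a kind of AE, the yearly rule for other SAEs does not fit Section 18.0.

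**The case against.** The strongest reply is that this is a minimal-risk behavioral pilot with several other routes for harm to surface. Staff are trained to contact the PI at once about any adverse event, with IRB notification if needed and no time limit (Sections 6.0 and 27.0). Unanticipated problems are reported under Section 20.0 whenever they occur. Interviewers debrief with the principal investigators (Section 21.0). Participants upset by questions can be reconnected with their psychosocial provider (Section 6.0). All of this stands. It limits the consequence, but it does not set the period for the AE form.

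A reader might go further than the text allows in four ways.
- **That adverse events cannot be compared between arms.** The analysis plan in Section 17.0 specifies no such comparison, and the DSMB reports are not described as by arm. If staff close controls at the debrief, the two windows roughly match. What can be said is that any tabulation by arm would depend on how staff read the control window.
- **That controls would be followed for AEs for 11 to 13 months against one visit in the intervention arm.** Nothing supports leaving the control window open to Visit 3. Section 6.0 uses the end of the intervention as a marker for all participants, which points to a Visit 1 close in both arms.
- **That distress at follow-up is lost altogether.** The channels above remain, and Section 19.0 itself names interviews and questionnaires as ways of noticing events. The documents do not establish that what is learned there never reaches the AE form, only that the rule does not require it for events beginning after the window.
- **That annual AE reporting to the IRB contradicts reporting as events arise.** Section 19.0 sets a yearly minimum for AEs, which prompt reporting satisfies. Only the rule for other SAEs is in tension.

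**Conclusion.** The point holds as a gap in the recording rule and a contradiction to be reconciled. As written, Section 19.0 does not require AE-form entry of any event that begins after the Visit 1 session in the intervention arm, gives controls no closing point, and does not match Section 18.0. In the intervention arm this leaves 2 of 3 visits and both interviews uncovered: about 110 interviews, 100 to 120 over the possible caregiver splits, or 81 to 97 at 81% follow-up. Those counts rest on full enrollment of 40 AYAs and 70 caregivers, and on at most two caregivers per AYA. They measure contacts outside the window, not harms. Given the expectation in Section 15.0 and the other channels, few serious events are likely to be missed. The change should be made because it is cheap and improves what the DSMB sees; the trial's efficacy results do not depend on it.

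**What to change.** Reconcile Sections 18.0 and 19.0 by stating one recording window for both arms: from each participant's own consent, whenever given, to completion of Visit 3, withdrawal or loss to follow-up. A common window can also be applied by staff who are blinded to arm under Section 6.0.

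After Visit 1, recording may be limited to events with a reasonable possibility of having been caused by study procedures (intervention, surveys or interviews). This keeps routine cancer-treatment events off the form for the following year. If that limit is adopted, the sentence requiring documentation regardless of relationship should be confined to Visit 1. The limit should be worded in terms of causal possibility, because the Related category in Section 19.0 also admits timing alone; rewriting that category is optional. The price of the limit is that a relatedness judgment then comes before recording.

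Separately, state one rule for when SAEs that are not both related and unexpected go to the IRB, so that Sections 18.0 and 19.0 agree.

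The cost is protocol wording and slightly more AE recording and assessment at visits already scheduled. No visit, sample size or efficacy analysis changes.

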20.0 Unanticipated Problems

Definition: This protocol uses the definition of Unanticipated Problems as defined by the Office for Human Research Protections (OHRP). OHRP considers unanticipated problems involving risks to participants or others to include, in general, any incident, experience, or outcome that meets all the following criteria:

- Unexpected in terms of nature, severity, or frequency given (a) the research procedures that are described in the protocol-related documents, such as the Institutional Review Board (IRB)-approved research protocol and informed consent document; and (b) the characteristics of the participant population being studied;
- Related or possibly related to participation in the research ("possibly related" means there is a reasonable possibility that the incident, experience, or outcome may have been caused by the procedures involved in the research); and
- Suggests that the research places participants or others at a greater risk of harm (including physical, psychological, economic, or social harm) than was previously known or recognized.

Reporting: Unanticipated problems (UPs) are reported by the PI to the Institutional Review Board (IRB) and the DSMB within 5 business days of discovery. SAEs are initially reported to NCI within five calendar days, with a full report filed within 10 calendar days.

21.0 **Provisions to Protect the Privacy Interests of Subjects**

Plan to Protect Participant Privacy: Participant confidentiality and privacy is strictly held in trust by the participating investigators, their staff, the safety and oversight monitor(s), and the funding agency. This confidentiality is extended to the data being collected as part of this study. Data that could be used to identify a specific study participant will be held in strict confidence within the research team. No personally-identifiable information from the study will be released to any unauthorized third party without prior written approval of the funding agency.

All research activities will be conducted in as private a setting, as much as possible.

Authorized representatives of the sponsor, study monitors, representatives of the Institutional Review Board (IRB), or regulatory agencies may inspect all documents and records required to be maintained by the investigator. The clinical study site will permit access to such records.

The study participant's contact information will be securely stored for internal use during the study. At the end of the study, all records will continue to be kept in a secure location for as long a period as dictated by the reviewing IRB, Institutional policies, or other requirements.

Study participant research data, which is for purposes of statistical analysis and scientific reporting, will be collected and maintained in REDCap, a secure electronic data capture system on the NCH research internet server. Individual participants and their research data will be identified by a unique study identification number. Other types of data (e.g., audio recordings from the interviews and intervention, paper surveys) may be kept in a locked cabinet within a locked office at the hospital or on an NCH computer. Interviews will be audio recorded and transcribed verbatim. Both the audio files and transcriptions will be stored on a secured intranet server only accessible by research staff. All identifying information will be removed from the transcripts and audio files will be deleted after data collection is completed. Only direct study personnel will have access to this information. The study data entry, study management systems, and related study files will be secured and password protected.

To help participants feel at ease and able to speak openly, study staff will be trained in active interviewing techniques (e.g. active listening, empathizing, proper body language). After interviews, staff will debrief with the principal investigators and address any issues that may have arisen during the interview.

To further protect the privacy of study participants, the Secretary, Health and Human Services (HHS), has issued a Certificate of Confidentiality (CoC) to all researchers engaged in biomedical, behavioral, clinical or other human subjects research funded wholly or in part by the federal government. Recipients of NIH funding for human subjects research are required to protect identifiable research information from forced disclosure per the terms of the NIH Policy (see https://humansubjects.nih.gov/coc/index). As set forth in 45 CFR Part 75.303(a) and NIHGPS Chapter 8.3, recipients conducting NIH-supported research covered by this Policy are required to establish and maintain effective internal controls (e.g., policies and procedures) that provide reasonable assurance that the award is managed in compliance with Federal statutes, regulations, and the terms and conditions of award. It is the NIH policy that investigators and others who have access to research records will not disclose identifying information except when the participant consents or in certain instances when federal, state, or local law or regulation requires

disclosure. NIH expects investigators to inform research participants of the protections and the limits to protections provided by a Certificate issued by this Policy.

- 22.0 Compensation for Research-Related Injury N/A
- 23.0 Economic Burden to Subjects

N/A

24.0 **Consent Process**

Consent forms describing in detail the study intervention, study procedures, and risks are given to the participant and written documentation of informed consent is required prior to starting any data collection procedures or randomizing the family. Families will be given a copy of the signed consent form for their records.

Caregivers will provide informed consent for their children aged 12-17 years, as well as themselves. Child participants who are 18 years old or older will provide consent for themselves. Children, aged 12-17, will additionally provide assent. Informed consent and assent (if applicable) will be obtained, prior to any study procedures taking place. During the process, the study will be described to participants and families will have the opportunity to discuss participation, before enrolling. Throughout the study, participants will be reminded of the voluntary nature of their involvement.

Consent will take place either in-person or via remote connection. In-person participants will each receive a copy of the consent form to follow along as the study staff reviews its content. The study staff will then collect all participants' signatures on a single form. Consent will be obtained from remote participant(s) by sending an electronic REDCap link via email. During the process, participants will be connected in via phone or Webex and will have the opportunity to discuss participation. Participants will be provided with an electronic copy of the consent form after submitting the REDCap version.

Trained study staff will obtain consent according to IRB policy, SOP: Informed Consent Process for Research (HRP-090) to ensure participants understand and do not feel coerced into consenting.

Waiver of Written Documentation of Consent (verbal) N/A

